### **15.3 Missing data**

Every effort will be made to avoid missing data. Nurses will be trained in data collection and the questionnaires filled out by them will be designed to minimise the amount of missing information possible. Missing data, where it does occur, will be investigated in order to determine the most appropriate strategy for dealing with it. The proposed strategies are: mean value imputation, last observation carried forward (potentially useful for missing diary data), as well as multiple imputation. Complete case analysis will also be presented so that the impact of missingness can be assessed. The main CACE analysis allows for the presence of missing data also.

### **15.4 Economic analysis**

The primary economic evaluation will be in the form of a cost effectiveness analysis (CEA) assessing total costs against the primary outcome (POEM).

The CEA will adopt a societal perspective. Parent/carer(s) time off work will be collected via additional questions to parent/carer(s) at the 4 week and 3 month follow-up points. All contacts with primary care (surgery consultations and home visits) and secondary care (including accident and emergency attendances, inpatient admissions and outpatient visits) and all drugs prescribed between baseline and 12 month follow-up will be collected from GP records at 12 months. All resources will be valued using standard methods . Unit costs will be mainly from national sources .

Mean differential costs will be estimated and assessed against mean POEM scores. As cost data are often skewed, tests for normality will be applied. If distributions are shown to be non-normal, non-parametric bootstrapping methods will be used to test for mean cost differences between groups . This approach will identify if any of the 3 treatments dominates (lower cost/higher effect) and is hence unambiguously the most cost effective. In the case of non-dominance, results will be reported as incremental cost effectiveness ratios showing the extra cost of achieving one extra unit of effect. A series of one way and multivariate sensitivity analyses will be undertaken to assess how sensitive results are to changes in the assumptions used.

The absence of published economic evaluations with POEM as the unit of effectiveness means that the cost effectiveness of oral/topical antibiotics relative to other treatments for eczema cannot be assessed. The study will, however, provide a benchmark for future studies i.e. any treatment with a cost per unit of POEM below those determined within CREAM will be more cost effective than oral/topical antibiotics.

Cost utility analysis (CUA) is the type of economic evaluation preferred by the National Institute for Health and Clinical Excellence (NICE) . CUA however, requires single index preference-based measures of health related quality of life to generate Quality Adjusted Life Years (QALY). Such analyses can produce incremental cost utility ratios (extra cost per extra QALY), which can then be assessed against the NICE threshold (currently £30,000 per extra QALY) to determine if the intervention is cost effective.

Given that participants in the CREAM study will be aged below 8 years, use of CUA as the main economic evaluation would be problematic. A recent systematic review of generic health related quality of life measures in children under 5 years

old concluded that none of the existing generic measures was both psychometrically and conceptually robust.

However, the Sheffield Health Economics Group has recently developed a condition specific preference-based HRQoL measure for children with atopic dermatitis, which is capable of generating QALYs but has not to date been tested within a clinical trial. CREAM provides an opportunity to test the new measure.

The economics of CREAM will thus also include an exploratory cost utility analysis. The study will attempt to identify the minimum age with which the new measure can be used. This will be done by:

- 1) Comparing the standard errors in responses by carers of children aged under X years with those above aged X years (X to be varied). The greater sensitivity of the measure when applied to older children should be reflected in lower standard errors.
- 2) As part of the 4-week face-to-face data collection parent/carer(s) will be asked two short questions to determine how difficult/meaningful they found the health utility questions. Responses from parents of younger/older children sub-groups will be compared.

While this element of the study will primarily be methodological development, exploratory incremental cost utility ratios will be produced using only NHS and personal social services costs as recommended by NICE for cost utility studies. Probabilistic techniques used to produce cost effectiveness acceptability curves showing the probability of the intervention falling below a range of willingness to pay thresholds e.g. the £30,000 per extra QALY used by NICE.

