### 8.1 Inclusion criteria

Children (aged 3 months to less than eight years) with atopic eczema (as defined by UK working party (Appendix I)) who are presenting with **a clinical suspicion of infected eczema**. This could include children where:

- The eczema is failing to respond to standard treatment with emollients and / or mild - moderate topical corticosteroids.
- There is a flare in the severity or extent of the eczema.
- There is weeping or crusting.

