## 14.4 Sample size calculation

Studies comparing active eczema treatments with placebo have generally found large effect sizes ( $>0.7$ ). There are no data available on the likely effect size identified by POEM. In a study of children with 'moderate to severe eczema' the median baseline POEM score was 13 (out of 28). Assuming a clinically important difference of 3 on the POEM score and a common standard deviation of 7, we estimate a meaningful effect size of 0.429. The main analysis will be a comparison of each active treatment with placebo. Therefore, using a significance of 0.025 (to allow for two comparisons), with 90% power, we would need 137 participants per treatment group (total 411). Allowing for 20% loss to follow-up we aim to recruit 516 participants (172 per centre).

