## **17 Trial closure**

For the purpose of regulatory and ethical requirements the end of the trial is defined as the date of the last data capture for the last participant undergoing protocol treatment.

Trial recruitment will end when 516 participants have been randomised, or at the request of the Trial Steering Committee or Independent Data Monitoring Committee.

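### Section 15.4 seeks the utility measure's minimum usable age by comparing standard errors, which depend on group size as well as spread, so the comparison can point to a wrong age

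*Protocol*

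**What the plan says.** Section 15.4 of the Protocol adds an exploratory cost-utility analysis built on a condition-specific preference-based measure that has not yet been tested in a trial. Within it, the Protocol sets a methodological question: "The study will attempt to identify the minimum age with which the new measure can be used".

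Two methods are given.

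- Item 1 is "Comparing the standard errors in responses by carers of children aged under X years with those above aged X years (X to be varied". The Protocol also says how the result is to be read: "The greater sensitivity of the measure when applied to older children should be reflected in lower standard errors".
- Item 2 uses the 4-week visit, where "parent/carer(s) will be asked two short questions to determine how difficult/meaningful they found the health utility questions". Answers are compared between younger and older subgroups.

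Section 15.4 does not adjust item 1 for group size, ask for equal-sized groups, or say that a standard deviation or a standard error of measurement is meant. It sets no threshold for calling the measure usable or unusable, and no rule for combining the two items.

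**The concern.** Item 1 fixes the statistic, the groups and the interpretation, so this is not detail left for an analysis plan. The statistic mixes two things: how variable the responses are, and how many children fall on each side of the cut. Only the first could say anything about the measure. Each change in X moves children from one group to the other, so the comparison changes even if the measure works identically at every age.

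At low X the younger group is small and its standard error is large. The expected finding, that the measure does better in older children, then tends to appear by construction. At high X the same mechanism works in reverse.

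There is a second difficulty. Even with group size removed, less spread is not the same as more sensitivity. If every carer gave the same answer the spread would be zero, and item 1 would rank that as the best performance. At stake is a minimum age, reported for a new instrument, that later users might adopt.

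**Working it through.** **Inputs.** Age range: "Children (aged 3 months to less than eight years) with atopic eczema" (section 8.1), so 0.25 to 8 years. Number followed up: "with 90% power, we would need 137 participants per treatment group (total 411" (section 14.4). Number randomised: 516 (section 17). The Protocol states no figure for the age comparison itself, and gives no age distribution and no SD for the utility measure.

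**The plan's own figure.** Section 14.4 uses a POEM difference of 3, SD 7, two-sided significance 0.025 (sidedness is not stated; the two-sided version fits) and 90% power. The normal formula gives 136 per group, and the t-test version gives 136.1, which rounds up to 137; 3 × 137 = 411. Then 137/0.80 = 171.25, rounded up to 172, and 3 × 172 = 516. The sample size reproduces.

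**Formula.** SE = SD/√n, so

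SE under X / SE over X = (SD under / SD over) × √(n over / n under).

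Total N cancels, so 411 and 516 give the same ratios.

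**No true difference.** Set SD equal on both sides and try two assumed age shapes:

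- (a) Ages spread evenly: ratio = √((8 − X)/(X − 0.25)). At X=2, √(6/1.75) = 1.85. At X=6, √(2/5.75) = 0.59.
- (b) Density declining linearly to zero at 8 years: share over X = ((8 − X)/7.75)². At X=3 this is (5/7.75)² = 0.416, and the ratio is √(0.416/0.584) = 0.84.

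| X (years) | (a) n under / over, N=411 | (a) SE ratio | (b) n under / over, N=411 | (b) SE ratio |
|---|---|---|---|---|
| 1 | 40 / 371 | 3.06 | 76 / 335 | 2.10 |
| 2 | 93 / 318 | 1.85 | 165 / 246 | 1.22 |
| 3 | 146 / 265 | 1.35 | 240 / 171 | 0.84 |
| 4 | 199 / 212 | 1.03 | 302 / 109 | 0.60 |
| 5 | 252 / 159 | 0.79 | 349 / 62 | 0.42 |
| 6 | 305 / 106 | 0.59 | 384 / 27 | 0.27 |
| 7 | 358 / 53 | 0.38 | 404 / 7 | 0.13 |

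A ratio above 1 would be read as the older group doing better. The ratio crosses 1 where the groups are equal in size: in (a) at (0.25 + 8)/2 = 4.125 years; in (b) at 8 − 7.75 × √0.5 = 2.52 years. Group size alone moves the ratio about 8-fold over X = 1 to 7 in (a) and about 16-fold in (b).

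**A true difference.** Suppose the SD really is 1.3 times larger in younger children (assumption), with shape (a). The SE ratio is then 1.3 × 1.85 = 2.41 at X=2, 1.3 × 0.79 = 1.03 at X=5, 1.3 × 0.59 = 0.77 at X=6 and 1.3 × 0.38 = 0.50 at X=7. The direction reverses at the two highest cuts although the true difference is constant.

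**Removing n.** The SD ratio is 1.00 at every X in the first case and 1.30 at every X in the second. That cures the artefact. It does not make low spread evidence of sensitivity, since low spread can also come from uniform severity or from a measure that does not respond.

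**The case against.** The best defence has four parts.

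- **No decision rule.** Section 15.4 only attempts to find an age, varies X, and sets no cut-off. A reader might infer from the ratios that the analysis would declare the measure a failure under 2 years, or must return a wrong age even with perfect data. The Protocol supports neither: there is no pass/fail criterion, and the SD also drives the standard error. This part stands.
- **The figures are illustrative.** The two age shapes put the crossing at different ages, so no particular age of reversal is established. This stands too. What holds under both shapes is that the direction changes where the groups are equal in size.
- **Spread carries some information.** If carers of older children answer with less noise, the SD could fall, which is presumably the Protocol's reasoning. But the SD could equally rise if the measure separates children better. The direction is ambiguous, which is a reason not to rest the conclusion on spread alone.
- **Little depends on it.** Item 2 is free of this fault, the work is labelled exploratory, and nothing says the age found will restrict who enters the cost-utility analysis. All true, but none of it repairs item 1.

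Perhaps a standard deviation or a standard error of measurement was meant, or analysts would read the standard errors beside the counts. The text says neither, so it would need changing in any case.

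**Conclusion.** The point holds in a limited form. As written, item 1 confounds the performance of the measure with the number of children each side of the cut, and can give a wrong minimum age. With equal SD the under-X/over-X ratio runs from 1.85 at X=2 to 0.59 at X=6 for evenly spread ages, and from 1.22 to 0.27 for ages skewed young. Both shapes are assumptions; the mechanism is not.

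A reader might also take the minimum age to be the stated purpose of the cost-utility work. It is not among the objectives in section 5.2, which list only the exploratory cost-utility analysis; the age question appears within section 15.4. The primary outcome, the sample size and the main cost-effectiveness analysis on POEM are unaffected. It is worth correcting because the instruction misleads if followed and the correction is cheap.

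**What to change.** Replace item 1 with responsiveness by age. Relate change in utility from baseline to 2 and 4 weeks to change in POEM and EASI over the same intervals, with an age interaction or within pre-set age bands, and report confidence intervals. Item non-response by age band is a useful optional addition. If spread is also reported, give SDs with confidence intervals rather than standard errors, and state that lower spread is not by itself evidence of sensitivity. Keep item 2 as it is.

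Table 1 already schedules health utility, POEM and EASI at baseline, 2 weeks and 4 weeks, so no new data are needed. The cost is a change of wording and slightly more exploratory analysis.

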## **16 Data storage & retention**

All research data will be kept until the youngest participant has reached the age of 21 or 15 years after completion of the trial (whichever is longer), in line with Cardiff University's Research and Development Framework guidance for clinical research. Archiving and access to archive will be managed in accordance with the standard operating procedures of the UK Clinical Research Collaboration (UK CRC) registered South East Wales Trial Unit (SEWTU). Electronic data will be stored confidentially on password-protected servers maintained on the Cardiff University Network. Paper records will be stored in appropriately labelled files in secure storage cabinets.

## **17 Trial closure**

For the purpose of regulatory and ethical requirements the end of the trial is defined as the date of the last data capture for the last participant undergoing protocol treatment.

Trial recruitment will end when 516 participants have been randomised, or at the request of the Trial Steering Committee or Independent Data Monitoring Committee.

## **18 Regulatory issues**

### **18.1 MHRA Compliance**

This trial has Clinical Trials Authorisation from the UK Competent Authority: MHRA. Reference 21323/0035/001-0001.

The sponsor, Cardiff University, will determine the level of monitoring required after assessing risk together with SEWTU. The trial will be conducted to International Conference on Harmonization Good Clinical Practice (ICH GCP). A EudraCT number and MHRA Clinical Trials Authorisation (CTA) will be obtained. We will meet all regulatory requirements to report adverse events, in particular Suspected Unexpected Serious Adverse Reactions (SUSARs). The Trial Manager will report SUSARs to the MHRA within 7 days for life-threatening and 15 days for non-life-threatening. Roles and responsibilities will be set ahead of Trial commencing. Trial drugs (branded pharmaceuticals and placebos) will be manufactured according to Good Manufacturing Practice (GMP) by the supplier of the branded products and placebo manufacturer, labelled according to Annex 13 and supervised and distributed by a Qualified Person (QP). All the staff involved in the Trial will be GCP trained and drug accountability logs maintained.

### **18.2 Ethical approval and Research Governance**

The CREAM trial will be conducted in accordance with the recommendations for physicians involved in research on human participants adopted by the 18th World Medical Assembly, Helsinki 1964 and later revisions.

Ethical approval was granted (Ref: 12/WA/0180) from the Multi-Centre Research Ethics Committee for Wales of the National Research Ethics Service via the Integrated Research Application System (IRAS). R&D approvals will be sought from the respective NHS Health Boards in Wales, England and Scotland. Clinical

Trial Authorisation will be sought from the Medicines and Healthcare products Regulatory Agency.

CREAM will be conducted according to the principles of good research practice (including proper and appropriate conduct of research, professional integrity, honesty, statistical methods, use of data interpretation of data, non plagiarism) and the Research Governance Framework for Health and Social Care. The Trial will comply with NHS Ethics Committees and Health and Safety regulations.

The Trial team will ensure all reports required to be submitted to the HTA and/or MHRA are completed and received within the specified time points (i.e. progress reports, annual reports, SUSAR reports, early termination/end of the Trial). Any substantial changes to the Trial will be sent to the HTA and/or MHRA for approval and non-substantial sent as notification only.

Full written consent will be obtained from those legally allowed to consent on children's behalf, and all research staff with participant contact will have passed Criminal Records Bureau checks.

All research data will be handled according to the principles of the Data Protection Act, especially for sensitive, personal data. Data will be anonymised and stored on a password protected computer located in secure University buildings and appropriately backed up.

### **18.3 Consent**

The study participants are young children (three months to less than eight years of age), and the parent/carer(s) will be asked to give written informed consent on behalf of their child for their child to take part in the study.

The study nurse will work closely with the parent/carer(s) to ensure appropriate consent to participation. The parent/carer(s) of children and the children will be informed about the trial through the Participant Information Sheet (PIS), pictorial booklets supplemented by verbal explanations from the research nurses. Randomisation (chance of receiving one of the trial arms), placebo and blinding will be explained in understandable terms in the PIS, which will be re-enforced by the trained research trial nurses. The PIS will also include details of any potential effects of not receiving an antibiotic along with the risks and benefits of the trial. All parent/carer(s) or those legally allowed to consent for the participants will be asked to provide written, informed consent before the trial commences. The parent/carer/legal representative(s) will be given as much time as they require to

ask questions and decide whether or not they would like their child to take part in the trial. Consent will only be considered informed following provision of adequate participant information.

The Trial Manager based in SEWTU will work closely with clinicians and research nurses to facilitate recruitment and appropriate administration of parent/carer(s) and participant information and consent documentation.

Any parent/carer(s) who does not consent to their child's participation in the trial will be made aware that not taking part will have no detrimental impact on their or their child's current and future healthcare and treatments. The parent/carer(s) will be made aware that they can withdraw their child at any stage without prejudice, and that withdrawal will have no detrimental impact on current and future treatments and health care.

#### **18.4 Confidentiality**

The Chief Investigators and the CREAM research team will preserve the confidentiality of participants in accordance with the Data Protection Act 1998. All data will be handled according to the principles of the Data Protection Act, especially for sensitive and personal data. Data will be anonymised and stored on a password-protected computer located in secure University buildings and appropriately backed up. Any data transfer across participant organisations will be closely monitored by a designated member of the trial team. A privacy risk assessment in each centre (Cardiff, Dundee and Bristol) will proactively identify and ameliorate risks of breaches of confidentiality and clearly designate the named individuals who will be allowed access to identifiable information. Published outcomes of the trial will not enable identification of the individual participants. All data will be retained for up to 15 years post trial closure in line with Cardiff University's procedures.

#### **18.5 Trial Indemnity**

Cardiff University will provide indemnity and compensation in the event of a claim by, and on behalf of participants, for negligent harm as a result of the study design and/or in respect of the protocol authors/research team. Cardiff University will not provide compensation for non-negligent harm.

The study will be conducted in accordance with SEWTU generic and study-specific operating procedures (SOPs) and work instructions. All trial related staff will be trained in those aspects of Good Clinical Practice (GCP) appropriate to their role in

the trial. Research Nurses will be trained in appropriate aspects of GCP (in particular, the informed consent process). The trial manager will visit the study sites to review compliance with the study protocol.

All applicants and clinical staff employed in a role that affects patient care will hold honorary contracts with the appropriate Health Board, conferring the protection of the NHS clinical negligence arrangements for staff.

Delegated responsibilities will be assigned to the NHS organisations taking part in this study.

## **18.6 Trial Sponsorship**

Cardiff University will act as sponsor for the trial. Delegated responsibilities will be assigned to the NHS Trusts and collaborating institutes (University of Dundee and University of Bristol) taking part in this trial.

## **18.7 Funding**

The CREAM trial is funded by the National Institute for Health Research (NIHR) Health Technology Assessment (HTA) programme (HTA Ref: 09/118/03).

## **18.8 Audits & inspections**

The trial is participant to inspection by the NIHR as the funding organisation. The study may also be participant to inspection and audit by Cardiff University under their remit as sponsor, and the MHRA.

# **19 Trial management**

## **19.1 Trial Management Group (TMG)**

The TMG will consist of the Chief Investigators, co-applicants and collaborators, Trial Manager, Trial Statistician and Trial Administrator. The role of the TMG is to help set up the trial by providing specialist advice, input in and comment on the trial procedures and documents (PIS, protocol etc) and advise on the promotion and the running of the trial. The group will meet monthly during the trial. This group will also review and advise on the reporting of SAEs. Additional meetings will be held on specific topics during the set-up phase covering data management and research nurse/clinical study officer training.

TMG members will be required to sign up to the remit and conditions as set out in the TMG Charter.

